#### 11.2.6 Exploratory Analyses

#### 11.2.6.1 Disease Control Rate

The DCR is the percentage of patients with a CR, PR, or SD lasting at least 12 weeks. The frequency and percentages of patients with a best overall response of CR, PR, SD lasting at least 12 weeks, SD lasting less than 12 weeks, or PD will be summarized.

The frequency of patients with CR, PR, SD for > 12 weeks will be compared between treatment groups using the Fisher's Exact Test.

#### 11.2.6.2 Tumor Growth Kinetics

The SLD measurements and/or other measures of tumor burden will be summarized as the percent change from baseline to each scheduled radiographic assessment using descriptive statistics (N, mean, standard deviation, minimum, median, and maximum). The mean percent changes at each scheduled visit will be compared between CO-1686 and erlotinib using the t-test.

In addition, the rate of change from baseline to the nadir and the rate of change from the nadir to disease progression will also be summarized for each treatment group and compared using the t-test.

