# 4.1.3 Exploratory Objectives

- To compare DCR of oral single-agent CO-1686 with that of erlotinib when administered as a first-line targeted treatment in patients with advanced/metastatic NSCLC whose tumors have EGFR-activating mutations
- To assess DCR in patients with baseline T790M mutations based on central allele-specific PCR EGFR mutation assay
- To compare kinetics of tumor growth between treatment arms measured by rate of change in sum of the longest diameters of target lesions (SLD) or rate of change of estimated or measured assessments of tumor volume
- To compare efficacy between treatment arms in patients with baseline T790M+ disease, detected using an ultra-sensitive research assay
- To compare the effect between treatment arms in patients who develop progressive disease (PD) while on study treatment but continue to receive assigned study treatment with CO-1686 or erlotinib beyond progression

- To evaluate concordance of EGFR mutation detection between patient tissue and plasma and to assess CO-1686 or erlotinib mediated alterations in levels of EGFR mutation detected using circulating tumor DNA (ctDNA) obtained from patient plasma
- To explore tissue and blood-based biomarkers that may be predictive of response or primary resistance to CO-1686 or erlotinib and investigate mechanisms of acquired resistance to treatment with CO-1686 or erlotinib using patient tumor tissue and blood samples

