Tumor assessments will be performed by the investigative site and scans will be evaluated locally for patient treatment decisions. Scans will also be collected, quality control performed, and stored with a central vendor; central reading of scans will not be done unless requested by the sponsor. Patients will be scanned at screening and every  $8 \pm 1$  weeks (Day 1 of Cycles 3, 5, 7, etc.) until there is radiographically-confirmed PD according to RECIST Version 1.1. If clinical progression is suspected, the confirmation of PD with a computed tomography (CT) scan or by magnetic resonance imaging (MRI) per RECIST Version 1.1 will be required. Patients who provide an optional additional consent will undergo tumor biopsy on progression and before subsequent-line therapy is initiated. Phase 2 patients randomized to the erlotinib treatment arm and who choose to participate in the crossover portion of the study after progression and are eligible to receive CO-1686, will undergo their optional biopsy after progression during the crossover. When protocol-specified therapy is discontinued, and the patient has yet to progress, patients will continue to undergo scheduled tumor assessments for monitoring of PFS. For all patients, after discontinuation of protocol-specified treatment, subsequent specific anticancer therapy used at the investigator's discretion will be recorded.

EGFR-inhibitor therapy is commonly continued beyond disease progression if the patient appears to be experiencing benefit in the investigator's opinion and this convention will be applied in this study. Patients may opt to continue to receive treatment with CO-1686 following radiographic progression as outlined in the National Comprehensive Cancer Network (NCCN) guidelines for treatment of NSCLC with EGFR-TKIs if: a) the patient provides additional consent, b) the investigator feels it is in the patient's best interest, and c) the sponsor provides approval. In general, eligible patients may include those with asymptomatic systemic progression or locally symptomatic progression, such as brain metastases amenable to local treatment, with

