## 9.6.2 Efficacy Evaluations

#### 9.6.2.1 Tumor Assessments

Tumor assessments will be performed at screening, and every  $8 \pm 1$  weeks thereafter (Day 1 of Cycles 3, 5, 7, etc.) until tumor progression, during the baseline period for patients who crossover (Phase 2 part only) to CO-1686 treatment following progression on erlotinib (scans obtained at progression may be used), and at the End-of-Treatment Visit. For patients with clinical progression, radiographic assessment should be performed to document evidence of radiographic progression. Tumor scans do not need to be repeated at end-of-treatment if < 2 weeks since last scan or the patient had disease progression at the last scan. An MRI may be used in place of a CT at end-of-treatment scan if required per local authorities. Scans will be evaluated locally for patient treatment decisions. Scans will also be collected and stored with a

central vendor and quality control performed; central reading of scans will not be done unless requested by the sponsor. Tumor response will be interpreted using RECIST Version 1.1 (Appendix A).

Patients who continue treatment with CO-1686 or erlotinib post-progression should continue to be scanned according to the protocol until they discontinue from the study.

Patients who discontinue treatment without progression should continue to be scanned every  $8 \pm 1$  weeks per protocol until disease progression occurs.

Tumor assessments should consist of clinical examination and appropriate imaging techniques (preferably CT scans of the chest and abdomen with appropriate slice thickness per RECIST Version 1.1); scans of the pelvis (CT or MRI) are required if there is prior evidence of local disease or if clinically indicated (symptomatic patients); other studies (MRI and X-ray) may be performed if required. The same methods used to detect lesions at baseline are to be used to follow the same lesions throughout the clinical study.

Brain imaging (CT/MRI) is required at baseline. Patients with brain lesions detected at baseline will not be eligible for the study. Brain imaging is not required on study unless clinically indicated.

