#### 11.2 Statistical Methods

#### 11.2.1 General Considerations

Quantitative variables will be summarized using descriptive statistics (N, mean, standard deviation, median, minimum, and maximum) and/or frequency and percentages for medically relevant categories. Categorical variables will be presented using frequencies and percentages.

Kaplan-Meier methodology will be used to summarize time-to-event variables. The number of patients with events and the number of censored patients will also be presented. The stratified logrank test will be used to compare the time-to-event distributions between the randomized treatment groups. The same variables used to stratify the randomization will be used in the stratified analyses. In addition, the Cox proportional hazards model will be used to estimate the HR between the randomized treatment groups.

The Fisher's Exact Test will be used to compare frequencies between treatment groups and the t-test will be used for comparing means between treatment groups.

All data will be used to their maximum possible extent but without any imputations for missing data. Results from Phase 2 and Phase 3 will be presented separately and pooled.

All statistical analyses will be conducted with the statistical analysis software (SAS®) system, Version 9.1 or higher.

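### Visit-by-visit t-tests of tumor size are open to informative dropout at later visits, because scanning usually ends at progression

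*Combined protocol and SAP*

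**What the plan says.** Section 11.2.6.2 summarizes SLD, or another measure of tumor burden, as percent change from baseline at each radiographic assessment. The test is then: "The mean percent changes at each scheduled visit will be compared between CO-1686 and erlotinib using the t-test". The same section compares two rates by t-test, baseline to nadir and nadir to PD; for the second, "the rate of change from the nadir to disease progression will also be summarized for each treatment group and compared using the t-test". Section 11.2.1 says data are used "without any imputations for missing data", and no longitudinal model for SLD is given.

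Under Section 5.1.2, scans are taken at screening and every 8 ± 1 weeks "until there is radiographically-confirmed PD according to RECIST Version 1.1". There are two exceptions. Patients who stop treatment without PD are scanned until PD. For those treated beyond PD, Section 9.6.2.1 says: "Patients who continue treatment with CO-1686 or erlotinib post-progression should continue to be scanned according to the protocol until they discontinue from the study". Section 5.1.2 presents this as ordinary practice that the study will follow: "EGFR-inhibitor therapy is commonly continued beyond disease progression if the patient appears to be experiencing benefit in the investigator's opinion". Section 11.2.6.2 does not say whether scans after PD enter the visit-wise test.

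Appendix A defines target-lesion PD as a rise of at least 20% (and at least 5 mm) over the smallest sum on study. New lesions and unequivocal non-target progression also count as PD. Comparing tumor growth kinetics is an exploratory objective (Section 4.1.3).

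**The concern.** The variable being compared largely decides who is measured next. A patient whose SLD has grown enough is called PD, contributes that scan, and then usually leaves the data. The arm that progresses faster loses more fast growers, so the patients still scanned become more alike across arms as follow-up lengthens. An observed-case t-test is unbiased only if absence at a visit is unrelated to tumor size, which cannot be assumed here. Section 3.3 hypothesizes more durable control through suppression of T790M, so the arms should separate at the later visits, where the test is weakest.

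The nadir-to-PD rate has a different problem. It is undefined for patients who have not progressed, so its t-test compares two subsets formed after randomization by the outcome itself. The comparison is no longer protected by randomization.

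**Working it through.** **Check of the planning figures.** Section 11.3 gives no power or effect size for kinetics; its nearest figure is for PFS. With 640 events, HR 0.80 and one-sided 0.025: z = (√640 / 2) × |ln 0.80| − 1.96 = 12.65 × 0.2231 − 1.96 = 0.86, so power is 80.6%. This matches the stated approximately 80%. The medians of 10 and 13 months from that section are used below.

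**Step 1: who is still due a scan.** Assume exponential PFS and no scans after PD. A patient is due a scan at week w if progression-free at week w − 8. With 4.348 weeks per month the medians are 43.5 and 56.5 weeks, and the share due is 0.5^((w − 8)/median). At week 48 this is 0.5^(40/43.5) = 53% for erlotinib and 0.5^(40/56.5) = 61% for CO-1686.

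| Week | Erlotinib | CO-1686 |
|---|---|---|
| 24 | 78% | 82% |
| 48 | 53% | 61% |
| 64 | 41% | 50% |
| 96 | 25% | 34% |

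**Step 2: effect on the planned test.** Each patient's SLD was simulated as a shrink-and-regrow curve, with PD at a 20% rise over nadir and growth calibrated to median PFS of 10 and 13 months. There were 100,000 patients per arm, with z standardized to 500 per arm. The curve shape and the spread of growth rates (log-SD 0.5, 0.8 or 1.1) are assumptions. The PD scan is kept in the test. Results for log-SD 0.8 with no scans after PD, as percent change from baseline, CO-1686 minus erlotinib in percentage points:

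| Week | Planned test, difference in means | All patients, difference in medians |
|---|---|---|
| 24 | -4.2 (z -2.3) | -5.3 |
| 32 | -3.1 | -7.2 |
| 40 | -1.3 | -9.3 |
| 48 | +0.3 | -11.4 |
| 64 | +1.8 (z 0.6) | -16.1 |

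Over log-SD 0.5 to 1.1 the planned difference at week 64 is +0.9 to +4.9 (z 0.3 to 1.5).

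**Step 3: like for like on geometric mean SLD.** CO-1686 relative to erlotinib, same setting:

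| Week | All patients | Scanned patients | Sequential regression on earlier scans (missing at random) |
|---|---|---|---|
| 48 | -20.2% | +1.7% | -16.1% |
| 64 | -26.1% | +6.3% | -17.5% |

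The likelihood-type analysis recovers 16.1/20.2 = 80% of the difference at week 48 and 17.5/26.1 = 67% at week 64. Early visits barely move: at log-SD 1.1, all versus scanned patients give -2.8% and -2.8% at week 8, and -6.9% and -5.9% at week 16.

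**Step 4: a second simulation.** This used 500 per arm, 300 trials, 23% slower regrowth on CO-1686 (1 − 10/13), 5% measurement error and exit at PD on observed SLD. True geometric mean ratios at weeks 24, 40 and 56 were 0.92, 0.85 and 0.78. Patients still scanned gave 0.93, 0.95 and 1.00, and a likelihood-based repeated-measures analysis gave 0.92, 0.85 and 0.79. Recovery is nearly complete because exit depended only on the modeled SLD.

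**Step 5: scans after PD.** The documents give no share scanned after PD. In the Step 2 model, with a random 30% scanned after PD, the week-48 planned difference is -6.1 to -20.2 points (z about -2.4 to -2.6) over the three log-SD values. With 60% it is -10.7 to -32.4 points (z -3.4 to -4.1). In both cases it favors CO-1686 at every visit.

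**The case against.** A reader might infer that the test uses only patients who have not progressed. The documents do not support that. The PD scan is itself a measurement that nothing in Section 11.2.6.2 excludes; in the Step 2 model, 27% (erlotinib) and 17% (CO-1686) of patients scanned at week 48 are at PD. Patients treated beyond PD also stay on the schedule.

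A reader might also infer that the plan will hide or reverse a true difference. That is not shown. In the second simulation the observed ratio reaches 1.00 but does not cross it. In the first, the sign changes from about week 48, only when nobody is scanned after PD, and never significantly.

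Other points stand too. The all-patient benchmark assumes SLD keeps evolving under assigned treatment after PD, a hypothetical quantity that the plan does not define. The baseline-to-nadir comparison does not require progression. Amendment 3 stops enrollment and leaves post-PD scans to the treating physician, so 500 per arm is a planning maximum.

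Post-PD scans do not fully rescue the plan. Step 5 continued patients at random, whereas Section 5.1.2 requires additional consent, a judgment that continuing is in the patient's interest, and sponsor approval. That is probably a favorable selection, so real recovery would be smaller. Section 8.1.1 also allows local treatment of lesions after PD, and Phase 2 erlotinib patients who crossed over were scanned on CO-1686.

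**Conclusion.** The concern holds as a risk of attenuation at later visits, with a possible but non-significant sign change if few patients are scanned after PD. The direction follows from the scan-stopping rule, the definition of PD and the absence of imputation. The size does not: it rests on assumed growth curves, an assumed spread of growth rates and an unknown share scanned after PD. The nadir-to-PD t-test is a comparison of post-randomization subgroups whatever those assumptions are.

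A reader might extend this to the trial's efficacy conclusion. That would be wrong: delayed progression is tested by the primary endpoint in Section 11.2.4.1, which does not use these t-tests, and no decision or alpha is attached to the kinetics analysis. This is a cheap improvement of low priority.

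**What to change.** In Section 11.2.6.2:

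- Make the between-arm comparison a likelihood-based repeated-measures or mixed-effects growth model of SLD, using all scans up to and including the PD scan, with arm-by-visit terms, baseline SLD and the randomization strata. A growth model also gives the rate of change named as the endpoint in Section 4.2.3.
- State a rule for zero SLD, which occurs when all target lesions disappear: for example log(SLD + constant), or model SLD or percent change directly.
- Exclude crossover scans, and use post-PD scans on assigned treatment only in a sensitivity analysis.
- Keep the visit-wise means and the nadir-to-PD rate as descriptive summaries, without a t-test.

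The cost is a wording change and slightly more programming; no new data are needed. The downside is reliance on a missing-at-random model. It reduces the bias but may not remove it all, for example when PD comes from new or non-target lesions that SLD does not capture.

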#### 11.2.6.3 Tissue and Blood Biomarkers

The change from baseline in tissue and blood biomarkers associated with the EGFR signaling pathway will be summarized with descriptive statistics and the t-test will be used to compare the mean changes between CO-1686 and erlotinib at each scheduled visit.

Both the time from randomization to the first observed increase in plasma mutant EGFR levels and the time from first observed increase in plasma mutant EGFR levels to disease progression will be summarized using Kaplan-Meier methodology.

11.2.6.4 Phase 2 Part Only: Subgroup of Patients that Crossover to CO-1686 from Erlotinib

The subgroup of patients that are initially randomized to erlotinib, experience a RECIST radiographic event of disease progression and test positive for the T790M mutation will be allowed to continue in the study after the initial event of disease progression and crossover to treatment with CO-1686.

The efficacy and safety of CO-1686 will be summarized descriptively in this subgroup of patients (treatment-emergent AEs, invPFS, ORR, DR, DCR and OS).

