## 4.2.3 Exploratory Endpoints

- DCR according to RECIST Version 1.1 as determined by investigator review
- DCR in patients with baseline T790M mutations confirmed by central EGFR mutation assay
- Rate of change in SLD
- Rate of change in tumor volume (measured or modeled)
- InvPFS, ORR, DR, DCR, time-to-treatment failure, and OS in patients who develop PD while on study treatment but continue to receive assigned study treatment with CO-1686 or erlotinib beyond progression
- Concordance of tumor and plasma ctDNA mutational analysis using contemporaneous samples
- Time from randomization to second observed increase over nadir in plasma mutant EGFR ctDNA levels (activating mutation, T790M mutation, either or both)
- Fraction of patients exhibiting disappearance of mutant EGFR ctDNA after initiating treatment with CO-1686
- Change from baseline in other tissue and blood biomarkers associated with the EGFR signaling pathways and relationship with clinical efficacy outcomes

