Biomarker analysis may be performed on a subset of patients if it becomes clear that the analysis will have limited scientific value in some patients (e.g., because of a very low titer of ctDNA), or if there are not enough serially collected samples from individual patients to allow for adequate biomarker evaluation.

For patients who provide additional consent and are randomized to CO-1686, genomic DNA will be extracted from a blood sample in order to detect genetic polymorphisms in CYP isozymes and to explore the possible correlation between CYP polymorphism and CO-1686 drug exposure.

Sample handling instructions will be provided in a separate laboratory manual.

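### Exploratory biomarkers are compared by an unadjusted t-test on mean change, which ignores baseline and can lose much of its power when a marker is right-skewed

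*Combined protocol and SAP*

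**What the plan says.** Section 11.2.6.3 starts with a summary: "The change from baseline in tissue and blood biomarkers associated with the EGFR signaling pathway will be summarized with descriptive statistics". It then states the between-arm comparison: "the t-test will be used to compare the mean changes between CO-1686 and erlotinib at each scheduled visit". It specifies no log scale, percent change, baseline covariate or rank-based test. Section 11.2.1 adds only the general rule that "the t-test will be used for comparing means between treatment groups".

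Two nearby sections are more specific. For tumor burden, Section 11.2.6.2 names the scale: "The mean percent changes at each scheduled visit will be compared between CO-1686 and erlotinib using the t-test". For EQ-5D, Section 11.2.4.2 compares change or percent change by ANCOVA with the baseline value as covariate.

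The endpoint list in Section 4.2.3 describes this item as "Change from baseline in other tissue and blood biomarkers associated with the EGFR signaling pathways and relationship with clinical efficacy outcomes". It gives ctDNA separate endpoints: tissue-plasma concordance, "Time from randomization to second observed increase over nadir in plasma mutant EGFR ctDNA levels", and "Fraction of patients exhibiting disappearance of mutant EGFR ctDNA after initiating treatment with CO-1686". Section 9.6.4 allows biomarker work to be limited to a subset of patients, for example "because of a very low titer of ctDNA".

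**The concern.** Because the neighboring section names percent change and this one does not, the natural reading is absolute change. If a marker is right-skewed and treatment acts proportionally, the patients with the highest baselines contribute most of the absolute change and most of its variance. A real proportional difference between arms can then be hidden by baseline spread. The baseline value is collected, so it could remove much of that noise, but the stated test does not use it as a covariate.

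At stake is whether an exploratory comparison reports no difference where one exists. The synopsis says the study will compare treatment effects on surrogate markers, and serial blood is drawn from all patients for this kind of question.

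**Working it through.** **1. Figure to reproduce.** There is none. The only power statement (Section 11.3) concerns PFS and has no bearing on biomarkers.

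**2. Inputs.** From Sections 6.1 and 11.3: about 100 per arm in Phase 2 and up to 500 per arm in Phase 3. Section 9.6.4 means the number analysed may be smaller. Assumed, because the documents are silent: log-normal levels with the same log SD *s* at baseline and follow-up; log-scale correlation ρ = 0.5; geometric mean follow-up-to-baseline ratios 0.25 and 0.15 (a 75% fall in one arm and a level 40% lower in the other, 0.25 × 0.6 = 0.15); two-sided 5%; complete data; no undetectable values.

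**3. Stated test, hand approximation.** Scale the median baseline to 1. Dividing through by e^(s²/2), the difference in mean change is 0.25 − 0.15 = 0.10. The variance of change in an arm with ratio *r*, divided by e^(s²), is

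V(r) = (1 + r²)(e^(s²) − 1) − 2r(e^(ρs²) − 1),

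so z = 0.10 / √{[V(0.25) + V(0.15)] / n} and power = Φ(z − 1.96) + Φ(−z − 1.96). With n = 100:

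- s = 0.5: V = 0.235 and 0.251; z = 0.10/0.0697 = 1.43; power about 30%.
- s = 1.0: V = 1.50 and 1.56; z = 0.10/0.175 = 0.57; power about 9%.
- s = 2.0: V = 53.8 and 52.9; z = 0.10/1.03 = 0.10; power about 5%.

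**4. Log-scale ANCOVA, hand approximation.** z = ln(0.25/0.15) / [s√(1 − ρ²)√(2/n)] = 0.511/(0.1225s). This gives 8.34, 4.17 and 2.09 at s = 0.5, 1.0 and 2.0, so power is about 100%, 99% and 55%.

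**5. Simulation under the same assumptions, 100 per arm.**

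| log SD | stated t-test | ANCOVA, original scale | ANCOVA, log scale |
|---|---|---|---|
| 0.5 | 30% | 100% | 100% |
| 1.0 | 8% | 86% | 98% |
| 2.0 | 2% | 14% | 54% |

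The simulation agrees with the hand figures. At log SD 2.0 the t-test falls below its nominal 5% because it is conservative with such heavy tails. At log SD 1.0 or less, baseline adjustment alone recovers most of the loss. At 2.0 the change of scale matters more.

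**6. Larger groups.** With 500 per arm, z for the stated test grows by √5 = 2.24, to 3.21, 1.28 and 0.22. Power is about 89%, 25% and 6%, against about 100% throughout for log-scale ANCOVA.

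**7. Other assumed effects.** A second model takes follow-up as baseline × ratio × log-normal noise and compares the raw-change t-test with a t-test on the log ratio. The noise log SD is 1.0, or equals the baseline log SD where that is smaller.

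- Ratios 0.8 and 0.6, 100 per arm: 90% against 98% at log SD 0.5; 22% against 53% at 1.0; 7% against 53% at 2.0.
- Ratios 0.20 and 0.10, 100 per arm: 80% at log SD 0.3, 20% at 1.0 and 5% at 2.0, each against nearly 100%.
- Ratios 0.20 and 0.10, 500 per arm: 98%, 65% and 11% at log SD 0.5, 1.0 and 2.0, each against 100%.
- Share of total absolute change carried by the top 5% of patients (100 per arm): 9% to 14% at log SD 0.3, 25% to 41% at 1.0, 57% to 64% at 2.0.
- No true difference: the raw-change t-test rejects in 2% to 5% of trials.

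**8. Does the test cover ctDNA levels?** Against: Section 4.2.3 gives ctDNA its own endpoints and assigns change from baseline to *other* biomarkers; the second paragraph of Section 11.2.6.3 handles plasma mutant EGFR by Kaplan-Meier. For: Section 11.2.6.3 drops the word *other*, and the Section 4.1.3 objective on treatment-related alterations in ctDNA levels has no other analysis of levels. The text does not settle it.

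**The case against.** The strongest reply is that the analysis is exploratory. It has no alpha, power claim or decision attached, and it errs toward missing a difference. Under the current amendment, development for NSCLC has stopped and the Extension Phase schedule has no serial biomarker blood draw. This stands, and it keeps the priority low.

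Mean absolute change is also a legitimate quantity, and absolute scale is inferred from silence. Both points stand, but they are reasons to state the scale; neither explains leaving out baseline.

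The log-scale figures are a best case, since no undetectable values were simulated. That is fair. Replacing undetectable values with half the detection limit can itself lose power when there are many, so it should not be the default remedy.

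A reader might go further and infer three things that the documents do not support:

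- **That ctDNA levels are t-tested.** This is an inference (step 8). The remark on low titer in Section 9.6.4 explains why patients may be left out; it does not describe the distribution of levels.
- **That the test has almost no power.** This holds only with strong skew or a steep fall in both arms. Across the assumed settings power runs from about 2% to 100%.
- **That its confidence interval would mislead or that false positives rise.** No interval is planned here, and type I error is not inflated.

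**Conclusion.** The point holds as a cheap improvement. The stated comparison ignores a collected baseline and, for right-skewed markers with proportional effects, can lose much of its power. With 100 per arm and the main assumptions, the loss relative to log-scale ANCOVA is about 70 percentage points at log SD 0.5 (30% against 100%), 90 at 1.0 (8% against 98%) and 52 at 2.0 (2% against 54%).

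These sizes rest on an SD, correlation and effect that the documents do not give. With mild skew the test can be adequate, and 500 per arm helps, but at log SD 1.0 even that size gives only 25% to 65% depending on the assumed effect. Coverage of ctDNA levels is an open question that the plan should answer.

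**What to change.** In Section 11.2.6.3, replace the t-test with ANCOVA of the post-baseline value on arm, baseline value and the randomization strata (EGFR mutation and territory). For right-skewed markers, use the log of both baseline and follow-up and report geometric mean ratios with 95% CI. Where many values fall below detection, use a rank-based comparison or compare the proportions detectable and undetectable, and state the rule for undetectable values in advance. Say explicitly whether ctDNA levels are included; if they are not, name the analysis that serves the Section 4.1.3 objective on ctDNA levels.

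The cost is SAP wording, with no new samples, visits or patients, and baseline-adjusted ANCOVA is already in the plan for EQ-5D. The downside is that results read as ratios instead of absolute changes, and that a convention for undetectable values is needed.
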